# Packaging

Brivaracetam tablets are manufactured, packaged, and labeled according to Good Manufacturing Practice (GMP) guidelines and applicable laws or regulations. The IMP is suitably packaged in such a way as to protect the IMP from deterioration during transport and storage.

7.3

### 7.4 Labeling

Clinical drug supplies will be labeled in accordance with the current International Council for Harmonisation (ICH) guidelines on Good Clinical Practice (GCP) and Good Manufacturing Practice and will include any locally required statements. If necessary, labels will be translated

Investigator (or designee) is responsible for the safe and proper storage of IMP at the site. Investigational medicinal product stored by the Investigator (or designee) is to be kent in a secured area with limited access according to the storage conditional designee.

Appropriate storage conditions must be ensured either by controlling the temperature (eg, room, refrigeration unit) or by completion of a temperature log in accordance with local requirements on a regular basis (eg, once a week), showing actual and minimum/maximum temperatures reached over the time interval.

In case an out-of-range temperature is noted, it must be immediately reported as per instructions contained in the IMP Handling Manual.

The Investigator (or designee) will instruct the subject to store the IMP following the instructions on the label.

### **Drug accountability** 7.6

A Drug Accountability form will be used to record IMP dispensing and return information on a by-subject basis and will serve as source documentation during the course of the study. Details of any IMP lost, damaged (due to breakage or wastage), not used, partially used, disposed of at the study site, or returned to the sponsor or designee must also be recorded on the appropriate forms. All supplies and pharmacy documentation must be made available throughout the study for UCB (or designee) to review.

Periodically, and/or after completion of the clinical phase of the study, all used (including empty containers)/partially used, unused, damaged, and/or expired IMP must be returned to UCB (or designee) preferably in the original package. Investigational medicinal product intended for the study cannot be used for any other purpose than that described in this protocol.

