### Procedures for monitoring subject compliance 7.7

The IMP (oral tablets) will be supplied to the subject/parent(s)/legal representative(s) at protocol specified time points according to the study schedule of assessments (Table 5-1).

The Investigator will instruct the subject/parent(s)/legal representative(s) to bring back at each visit the kits (even empty) dispensed at the previous visit and containing all the remaining tablets of study medication.

The subjects/parent(s)/legal representative must record the situation of medication compliance every time the subjects take an IMP.

Drug accountability must be done in the subject/parent(s)/legal representative(s) presence in order to obtain explanations regarding discrepancies in compliance with the dosing regimen. Drug accountability must be recorded on the Drug Accountability form.

Brivaracetam

Compliance with investigational product is defined as investigational product consumption by the subject within 80% and 120% of the prescribed dosage. If a subject is found to be persistently noncompliant (<80% or >120%), the Sponsor in conjunction with the Investigator will make a decision as to whether the subject should be withdrawn from the study. 1.ation

The number of tablets dispensed and returned must be recorded in the source documents.

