### 8.11 **Unscheduled Visit (if applicable)**

authorization bjecto Jany At any time, the subject may have an additional study visit if the Investigator or the subject and/or legal representative deem it necessary. All information, including reason for visit, any information on AEs, etc, should be collected in the source documents and recorded in the appropriate sections of the eCRF.

If an Unscheduled Visit is conducted due to safety or efficacy reasons, a C-SSRS assessment will be performed with the subject during the visit. If an Unscheduled Visit is conducted for reasons other than safety or efficacy concerns (eg, replacement of lost medication, repeated collection of a laboratory specimen due to collection or analysis issues), a C-SSRS will not be required at these visits.

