3.9.5 Time to *n*th partial seizure

The evaluation of time to n^{th} partial seizure is based on the relative day of occurrence of the n^{th} partial seizure (n=1, 5, and 10) during the Treatment Period. Only seizure DRC data from the randomization up to and including the last visit of the Treatment Period will be considered. The algorithms described in Section 3.9.2 also apply to this analysis.

The time to n^{th} seizure will be calculated as the date of the n^{th} partial seizure minus the date of randomization plus 1 day for subjects who have at least n partial seizures in the Treatment Period. Subjects with fewer than n partial seizures during this period will be addressed as follows:

- Subjects who complete the Treatment Period will be analyzed as censored cases with date of censoring (ie, analyzed as non-events) based on the date of last dose of IMP during the Treatment Period.
- Subjects who discontinue due to lack of efficacy during the Treatment Period will be analyzed as having the nth seizure (i.e. as an event) on the date of last dose of IMP during the Treatment Period.
- Subjects who discontinue for reasons other than lack of efficacy during the Treatment Period will be analyzed as censored cases with date of censoring based on the date of last dose of IMP during the Treatment Period.

For those cases, time to censoring or time to event will be calculated as the date of last dose of IMP during the Treatment Period minus the date of randomization plus 1 day.

3.9.6

Dose mapping for total daily BRV dose

During the Treatment Period, subjects are to take 3 tablets twice per day (morning and evening) except for the first day where they will only take the evening dose, and the last day where they will only take the morning dose.

The 3 tablets will consist of: 2×50 mg BRV tablets and 1×25 mg PBO tablet for subjects randomized to the BRV 200mg treatment group; 1 × 25mg BRV tablet and 2 × 50mg PBO tablets for subjects randomized to the BRV 50mg treatment group; 2×50 mg PBO tablets and 1 × 25mg PBO tablet for subjects randomized to the PBO group, as shown in Table 3.1.

Table 3.1: Doses of individual BRV and PBO tablets during the Treatment Period

| | | Individua | l tablet co | ntents and | dose (mg) | |
|-----------------|--------|-----------|-------------|------------|-----------|--------|
| Treatment group | | Morning | | | Evening | |
| BRV 200mg/day | BRV 50 | BRV 50 | PBO 25 | BRV 50 | BRV 50 | PBO 25 |

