In the drug dosing log CRF the daily total blinded dose (BRV + PBO) is recorded. The appendix Section 12.1 describes how to determine the daily BRV dose and number of tablets taken using the total blinded dose for each treatment group. It should be noted that when a subject is on 200mg BRV or 50mg BRV treatment and if subject takes less than the number of tablets per day they are supposed to take, it is unknown whether they missed an active or placebo treatment. It is assumed that the subject took the active treatment before PBO. For example, suppose a BRV 200mg subject used 3 tablets on a study day during the Treatment Period, and this day was not their first or last day during the Treatment Period, it would be assumed that the subject used the 3 × 50mg BRV tablets so would have a BRV quantity of 150mg BRV tablets.

If a subject on 200mg BRV or 50mg BRV treatment exceeds the number of tablets per day they are supposed to take, it is assumed they begin retaking the tablets for the same study day, and it is assumed that the subject took active treatment before PBO for the additional tablets. For example, suppose a BRV 200mg subject used 7 tablets on a study day during the Treatment Period, and this day was not their first or last day during the treatment period, it would be assumed that the subject used the 4×50 mg BRV tablets and 2 PBO tablets they were supposed to take on the study day, and an additional active treatment of 50mg so they would have a BRV quantity of 250mg BRV tablets.

In the circumstance the daily total blinded dose as recorded on the CRF exceeds the maximum nominal dose as described in the appendix Section 12.1, it is assumed the subject took the active treatment for all additional dosage. For example, suppose a BRV 200mg subject was recorded 275 mg/day total daily dose during the treatment period on the CRF (exceeding the maximum dose of 200 mg/day during the treatment period), it would be assumed the subject took active 200mg + 75 mg = 275 mg/day.

.10 Changes to protocol-defined analyses

Not applicable

S3.11

Consideration for COVID-19

A new COVID-19 CRF, to evaluate the impact of global pandemic was created and implemented to collect the information on impacted visit, impact category, and relationship to COVID-19.

The relationship to COVID-19 global pandemic will be assessed and captured in CRF form COVID-19 Impact: "Relationship to COVID-19" as: confirmed COVID-19 infection, suspected

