7 MEASUREMENTS OF TREATMENT COMPLIANCE

IMP compliance (%) will be calculated according to the definition shown in the formula below;

Compliance(%) =
$$100 \times \frac{\text{Number of tablets taken}}{\text{Number of tablets that should have been taken}}$$

In general, for a duration where the number of tablets which should be taken per day is constant, the compliance is represented as follows;

Compliance(%) =
$$100 \times \frac{(\text{Number of tablets dispensed}) - (\text{Number of tablets returned})}{(\text{Number of tablets per day}) \times (\text{Number of days in the duration})}$$

If a period where the number of tablets which should be taken per day may not be constant, the compliance will be calculated as a weighted sum of compliance of each duration weighted by length of the duration.

Compliance(%) =
$$100 \times \sum_{i} (C_i \times W_i)$$
,

where *i* represents a duration with a constant number of tablets per day,

(Number of tablets dispensed for *i*)-(Number of tablets returned for *i*)

$$C_i = \frac{1}{(\text{Number of tablets per day for } i) \times [(\text{End date of } i) - (\text{Start date of } i)]'}$$

$$W_i = \frac{(\text{End date of } i) - (\text{Start date of } i)}{(\text{End date of Period}) - (\text{Start date of Period})^2}$$

Note that the first and last day of treatment are considered as half days because the start day of each duration will contribute evening only and the last day of it will contribute morning only.

For a period where treatment is double-blind, the number of tablets which should been taken per day is defined in Table 3.1, Table 3.2 and Table 3.3.

For instance, total planned tablet number during the Treatment Period will be calculated as 6 times the number of days from the first dose of IMP (Visit 3) up to the last visit in the period (EDV for early discontinuers, Visit 7 otherwise).

Brivaracetam

Compliance for Treatment Period (%)

$$= 100 \times \frac{(\text{Number of tablets dispensed}) - (\text{Number of tablets returned})}{6 \times [(\text{Date of EDV or Visit 7}) - (\text{Date of Visit 3})]}$$

orization For the overall compliance which consists of the Treatment Period and either the Transition Period or the Down-Titration Period, the denominator of the formula for W_i is represented as [(the latest date of EDV, Visit 7 and Visit 8) – (Date of Visit 3)].

For the Open-Label Temporary Period,
$$C_i$$
 can be applied for the above formula as only BRV
25mg tablet will be used.

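### SAP 7 counts tablets documented as lost as taken, so a fully compliant subject with one replaced 4-week supply is tabulated at 133% (minor; descriptive compliance table only)

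*Protocol*

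**What the plan says.** SAP 7 opens with a definition based on intake: "IMP compliance (%) will be calculated according to the definition shown in the formula below", namely tablets taken over tablets due, times 100. The formulas that follow replace intake by an accountability count. The general form uses dispensed minus returned. The weighted form for periods with a varying tablet number has the numerator "Number of tablets dispensed for *i*)-(Number of tablets returned for *i". The worked Treatment Period formula and the Open-Label Temporary Period formula use the same difference. For the denominator, the "total planned tablet number during the Treatment Period will be calculated as 6" times the days from Visit 3 to Visit 7 or the EDV.

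The protocol expects some tablets to be neither swallowed nor returned:

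- Protocol 7.6 requires "Details of any IMP lost, damaged (due to breakage or wastage), not used, partially used" to be recorded, along with IMP disposed of at the site.
- Protocol 8.11 gives as one reason for an Unscheduled Visit: "eg, replacement of lost medication".
- Protocol 7.7 tells subjects to "bring back at each visit the kits (even empty) dispensed at the previous visit". It defines compliance as consumption between 80% and 120% of the prescribed dosage.

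SAP 7 tabulates compliance on the Safety Set as <80%, 80% to 120% and >120%, and lists it by subject.

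**The concern.** Dispensed minus returned equals intake only if every tablet not taken comes back. A lost tablet does not come back, so the formula counts it as swallowed. If it is replaced, the replacement enters the dispensed count as well. The protocol has such losses documented, so the plan would ignore information it asks sites to collect and would depart from its own definition.

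At stake is the planned compliance result. It uses the protocol's own limits, and a lost supply would look like excess intake. A reader of the table could not tell the two apart.

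**Working it through.** The documents give no compliance result to reproduce. The one planned figure that can be checked is the multiplier of 6. SAP 3.9.6 states that "subjects are to take 3 tablets twice per day (morning and evening"), and 3 × 2 = 6 tablets a day, so it agrees.

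**Inputs**

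- Treatment Period: 12 weeks = 84 days (Protocol 5.1, SAP 2.3.1).
- Tablets due: 84 × 6 = 504.
- Visits at Weeks 0, 2, 4, 8 and 12 (Protocol Table 5–1). A 2-week supply is 14 × 6 = 84 tablets and a 4-week supply is 28 × 6 = 168. Kit sizes are not stated, so these are inferred from the visit spacing. Covering the 3-day visit window would make the larger supply 31 × 6 = 186.
- Number of tablets lost, L: an assumption, shown as a range.

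**SAP figure for a fully compliant subject whose loss is replaced**

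Dispensed = 504 + L, returned = 0, truly taken = 504.

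SAP compliance = 100 × (504 + L) / 504; true compliance = 100%. The overstatement is 100 × L / 504 percentage points.

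| Tablets lost and replaced | SAP figure | True | SAP category |
|---|---|---|---|
| 84 (2-week supply) | 588/504 = 116.7% | 100% | 80% to 120% (correct) |
| 102 (17 days) | 606/504 = 120.2% | 100% | >120% (wrong) |
| 168 (4-week supply) | 672/504 = 133.3% | 100% | >120% (wrong) |
| 186 (31 days) | 690/504 = 136.9% | 100% | >120% (wrong) |

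**Threshold.** The category is wrong once L exceeds 0.2 × 504 = 100.8 tablets, which is 100.8 / 6 = 16.8 days of supply. A subject whose true compliance is already above 100% crosses the upper limit with fewer.

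**Sensitivity to period length.** With 168 tablets lost and replaced, an 81-day period (486 due) gives 654/486 = 134.6% and an 87-day period (522 due) gives 690/522 = 132.2%.

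**With documented losses subtracted.** (672 − 0 − 168) / 504 = 100.0%, the true value.

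**The case against.** **Convention and safeguards.** Dispensed minus returned is introduced as the general case under a definition that speaks of tablets taken. Protocol 7.7 has accountability done with the subject present so that discrepancies are explained. The blinded data evaluation meeting reviews data quality and outliers, so a value of 133% would probably be looked at. This lowers the risk but does not remove it: the Treatment Period formula is written out in full, and nothing says how an explained loss changes the number.

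**Size and reach.** The 133% example needs a whole 4-week supply to be lost and replaced, and a 2-week supply moves no fully compliant subject across a limit. Compliance is a descriptive Safety Set summary. These points stand and limit the severity.

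**Stronger readings that the documents do not support.**

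- A reader might infer that the formula also hides under-dosing. For example, a subject takes half the tablets over the last 8 weeks and keeps those kits. True intake is (168 + 0.5 × 336)/504 = 336/504 = 67%, and the figure shown would be 504/504 = 100%. That requires a kit not brought back to be entered as zero returned. SAP 7 gives no such rule; the return count could equally be missing and leave compliance missing. What can be said is that the SAP is silent on unreturned kits.
- A reader might infer that the efficacy result is affected. The primary ANCOVA on the FAS does not use compliance. A link to the Per-Protocol Set would depend on the separate IPD specification, which is not in the documents.
- A reader might think the dosing log settles the matter. SAP 3.9.6 says: "In the drug dosing log CRF the daily total blinded dose (BRV + PBO) is recorded". It refers to SAP 12.1 for both dose and tablet number, but Table 12.1 converts blinded mg only to BRV mg, notes entries with two possible doses, and has no Down-Titration rows. It cannot reliably supply tablet counts for every period.

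**Conclusion.** The point holds as a minor one. For tablets documented as lost, the SAP 7 formulas give a figure that contradicts the SAP's own definition, too high by 100 × L / 504 percentage points over a full Treatment Period. One lost and replaced 4-week supply turns 100% into 133% and moves the subject into >120%. Below about 101 lost tablets, a fully compliant subject stays in the correct category.

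This rests on three assumptions: a full 84-day period, supply sizes inferred from the visit spacing, and lost tablets not entering the returned count. The documents give no frequency of loss, so the figures show what can happen, not what to expect. The consequence is confined to the compliance table and listing.

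**What to change.** In SAP 7, for the general, C_i, Treatment Period and Open-Label Temporary Period formulas, set:

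tablets taken = dispensed − returned − tablets documented as lost, damaged or discarded **and not already counted as returned**.

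The condition matters. Protocol 7.6 has damaged IMP sent back to the sponsor and separately records IMP disposed of at the site, so some of these tablets may already be in the returned count. State that each tablet is subtracted once, and name the accountability record as the source.

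Where a kit was not brought back and no count is documented, do not treat it as zero returned. Set compliance for that interval to missing, flag the subject in the listing, and show the dosing log only as supportive information.

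Cost: a short SAP rule and some programming. The protocol does not say whether loss counts reach the eCRF, so they may have to be transferred from the accountability form, and a few intervals will have missing compliance.

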### Procedures for monitoring subject compliance 7.7

The IMP (oral tablets) will be supplied to the subject/parent(s)/legal representative(s) at protocol specified time points according to the study schedule of assessments (Table 5-1).

The Investigator will instruct the subject/parent(s)/legal representative(s) to bring back at each visit the kits (even empty) dispensed at the previous visit and containing all the remaining tablets of study medication.

The subjects/parent(s)/legal representative must record the situation of medication compliance every time the subjects take an IMP.

Drug accountability must be done in the subject/parent(s)/legal representative(s) presence in order to obtain explanations regarding discrepancies in compliance with the dosing regimen. Drug accountability must be recorded on the Drug Accountability form.

Brivaracetam

Compliance with investigational product is defined as investigational product consumption by the subject within 80% and 120% of the prescribed dosage. If a subject is found to be persistently noncompliant (<80% or >120%), the Sponsor in conjunction with the Investigator will make a decision as to whether the subject should be withdrawn from the study. 1.ation

The number of tablets dispensed and returned must be recorded in the source documents.

### 7.8 Concomitant medication(s)/treatment(s)

For any treatment other than the IMP, including over-the-counter products, an accurate record must be kept in the source documents and in the eCRF.

All concomitant medications should be recorded in the eCRF at the Screening Visit and subsequently be recorded only if there is a change regarding the administration of the medication. For all subjects, new medications should be recorded in the eCRF at only the first visit at which they are reported and subsequently only if there is a change. For any change, the start date corresponding to the date of change in administration should be recorded in the eCRF.

For all subjects, all changes in concomitant AEDs and non-AEDs will be recorded on the AED or non-AED concomitant medication page, respectively, in the eCRF. This record should include the name of the drug (preferably the brand name), the dose, the date(s) of administration, formulation(s), and the indication for use.

### 7.8.1 Permitted concomitant treatments (medications and therapies)

All subjects will take 1 or 2 concomitant AEDs (Appendix 3 [Section 17.3]). Only oral-daily use is permitted (any other use or route of administration is prohibited, except when it is used as rescue medication).

All concomitant AEDs except the ones specified in Section 7.8.2 are permitted during the study. All AEDs need to be at a stable dose for at least 4 weeks prior to Visit 1 and kept stable over the whole study period.

If the subject discontinues from the study, the above limitation is not required after the Early discontinuation Visit (EDV), considering subject safety.

Drugs with no CNS effects, which are not strong enzyme inducers/inhibitors, are allowed.

Vagal nerve stimulation is allowed and will be counted as a concomitant AED.

### Prohibited concomitant treatments (medication and therapies) 7.8.2

The following concomitant medications/treatments are prohibited during the study:

BRV (other than IMP)

Potassium bromide, sodium bromide, and calcium bromide

- Other investigational products and drugs and medical devices that have not been approved in each country
- Brain surgery (including surgery for examination purposes).

# 7.8.3 Restricted concomitant treatments (medications and therapies)

The following concomitant medications/treatments are restricted during the study:

- Drugs with possible CNS effects (anxiolytics, hypnotic, and neuropsychiatric agents) including benzodiazepines are allowed if at stable dose from at least 4 weeks prior to Visit 1 and during the entire study period. In case of as-needed use, it is allowed the frequency is up to once a week in this study. However, it is prohibited to take more than once a week in this study. Any drug where the route of administration is not oral, except when it is used as rescue medication.
- Any drug that significantly influences the metabolism of BRV (cytochrome P450 strong inducers such as rifampin/rifampicin) are allowed if at stable dose from at least 4 weeks prior to Visit 1 and during the entire study period.

